#### **5.4.5 Selection and Timing of Dose for Each Patient**

All study drug will be administered orally once daily. Patients who meet all eligibility criteria at the Screening and Pretreatment Visits will be randomized to treatment at the Randomization Visit (randomization number assigned by IWRS) and dispensed two bottles, one containing 35 tablets and one containing 35 capsules. Additional bottles will be dispensed at subsequent visits per the Schedule of Evaluations ([Table 1](#)). Patients will be instructed to take one tablet and one capsule in the morning at least 30 minutes before breakfast. Patients will take their initial dose of study drug (one tablet and one capsule, as described in [Section 5.4.1](#)) at the study center during the Randomization Visit. Patients must have fasted for at least 2 hours prior to arriving at the clinic for this visit. Patients will be instructed to return all unused study drug and bottles to the study center at the visits defined in the Schedule of Evaluations ([Table 1](#)).

#### **5.4.6 Blinding**

This study is a double-blind, double-dummy study.

A list of patient randomization codes will be generated by Actavis, and implemented by the IWRS vendor (an electronic version will be stored on a secure server). This list will identify each patient by randomization number and include the patient's corresponding treatment assignment. The medication code list will be supplied by Almac Clinical Services to the IWRS contract research organization.

In case of an emergency, the IWRS will be accessed to obtain the study drug assignment of a patient. Accessing the IWRS for emergency unblinding should be done only in an emergency that necessitates identifying the study drug for the welfare of the patient, and only after unsuccessfully attempting to contact the Medical Monitor or designee. If the blind is broken, the study center will notify the Ironwood contact (see the [Study Identification](#) information in the Synopsis) immediately. An explanation for breaking the blind will be recorded on the relevant eCRF. Breaking the code at the study center will disqualify the patient from further participation in the study.

#### **5.4.7 Concomitant Medicines**

A complete list of drugs that are conditionally allowed and drugs that are not allowed as concomitant medicines for either episodic or chronic use or as Rescue Medicine is provided in [Appendix II](#). During the Pretreatment and Treatment Periods, patients may use dispensed, protocol-permitted laxatives (bisacodyl tablets or suppositories) as Rescue Medicine when at least 72 hours have passed since their previous BM or when their symptoms become intolerable. In order to qualify for randomization into the Treatment Period, patients must not have used Rescue Medicine on the calendar day before the Randomization Visit and on the day of the Randomization Visit up until the time of the clinic visit. Patients must agree to refrain from using Rescue Medicine from the time they arrive at the clinic for the Randomization Visit through the calendar day after randomization.

At the Screening Visit, all ongoing medicines or investigational products taken by the patient, and past use of certain IBS-C or CIC (approved or unapproved) prescription medications

(including tegaserod [Zelnorm®], prucalopride, plecanatide, linaclotide [Linzess®] and lubiprostone [Amitiza®]), even if not ongoing at the time of the Screening Visit, will be recorded. Any over-the-counter or prescription laxatives, suppositories, or enemas used to treat IBS-C may not be used during the Pretreatment and Treatment Periods and may not be used on the calendar day before the Pretreatment Visit. Other prohibited medicines may not be used during the Pretreatment and Treatment Periods and may not be used during the 14 calendar days before the Pretreatment Visit (refer to [Appendix II](#)). Thereafter, any changes in concomitant medicines or new medicines added will be recorded on the eCRF. Concomitant medicines will be recorded at study visits throughout the entire study. Rescue Medicine will be documented by the patient via eDiary.

#### **5.4.8 Treatment Compliance**

Study drug will be administered to the patient by study center staff at the Randomization Visit. For all other days in the Treatment Period, study drug will be taken by the patient once daily in the morning at least 30 minutes before breakfast. Study drug compliance by the patient will be closely monitored during the Treatment Period by counting the number of tablets/capsules returned and recording that information on the eCRF. Every effort will be made to collect all unused study drug.

### **5.5 EFFICACY AND SAFETY VARIABLES**

#### **5.5.1 Schedule of Evaluations**

The schedule of study procedures and assessments is presented by visit in the Schedule of Evaluations in [Table 1](#). The descriptions of the procedures to be performed at each visit are provided below. Following randomization, all visits should adhere to a window of  $\pm 3$  days during the Treatment Period, except for the EOT Visit, which cannot occur before Day 85.

**Table 1. Schedule of Evaluations**

Schedule of Evaluations MCP-103-204							
	Screening Period (Up to 21 days)	Pretreatment Period (14 to 21 days)	Treatment Period (12 weeks)				
Visit Days →	Screening Visit (Day -42 through Day -15)	Pretreatment Visit (Day -21 to Day -14)	Randomization Visit (Day 1)	Follow-up Call (Day 3)	Week 4 Visit (Day 29±3)	Week 8 Visit (Day 57±3)	Week 12/End-of-Treatment Period Visit o (Day 85+3)
Visit Numbers →	Visit 1	Visit 2	Visit 3		Visit 4	Visit 5	Visit 6
Study Procedure ↓							
Signature of ICF	X						
Inclusion and Exclusion Criteria Verification	X	X	X				
IWRS Registration a	X	X	X		X	X	X
Medical History	X						
Physical Examination b	X						X
Body Weight and Height c	X	X	X		X	X	X
Seated Vital Signs d	X	X	X		X	X	X
Prior and Concomitant Medicines e	X	X	X		X	X	X
Clinical Laboratory Tests f	X		X				X
Pregnancy Test g	X		X				X
Laxative/Suppository/Enema Washout Instructions h	X						
AE Evaluations i		X	X	X	X	X	X
eDiary Registration and Training j		X	X		X	X	X

**Table 1. Schedule of Evaluations**

Schedule of Evaluations MCP-103-204							
	Screening Period (Up to 21 days)	Pretreatment Period (14 to 21 days)	Treatment Period (12 weeks)				
Visit Days →	Screening Visit (Day -42 through Day -15)	Pretreatment Visit (Day -21 to Day -14)	Randomization Visit (Day 1)	Follow-up Call (Day 3)	Week 4 Visit (Day 29±3)	Week 8 Visit (Day 57±3)	Week 12/End-of-Treatment Period Visit o (Day 85+3)
Visit Numbers →	Visit 1	Visit 2	Visit 3		Visit 4	Visit 5	Visit 6
Study Procedure ↓							
Daily and Weekly Assessments k		X	X		X	X	X
eDiary Compliance Verification and Reminder l			X		X	X	X
Rescue Medicine Dispensed m		X	X		X	X	
Patient eDiary Entry, in Clinic			X		X	X	X
Randomization			X				
SF-12v2			X		X	X	X
EQ-5D			X		X	X	X
SF-MPQ-2			X		X	X	X
IBS-SSS			X		X		
Treatment Satisfaction Assessment					X	X	X
Study Drug Dispensed			X		X	X	
Study Drug Administration n			X				
Study Drug Accountability					X	X	X

a. Site personnel will interact with IWRS to register the patient visit. Refer to the IWRS User Manual.

- b. A physical examination includes the following: general appearance, HEENT (head, ears, eyes, nose, and throat), neck, cardiovascular, thorax/lungs, breasts, abdomen, rectal, genitourinary, musculoskeletal, lymph nodes, skin, neurologic, and mental status. A rectal examination should be performed during the Screening Period on all patients who do not require a colonoscopy (refer to [Appendix III](#)). After the Screening Period, the rectal examination is optional and may be performed at the discretion of the investigator. Breast and genitourinary examinations are optional at the discretion of the investigator.
- c. Height is measured only at the Screening Visit.
- d. Vital signs must be obtained in the seated position and include oral temperature, respiratory rate, blood pressure, and pulse.
- e. At the Screening Visit, information related to concomitant medicine that patients are taking on the day of the visit will be captured as well as their history of using particular treatments for IBS-C and CIC (see Section [5.4.7 Concomitant Medicines](#)).
- f. Chemistry, CBC, and drug screen. The urine drug screen will be performed at the Screening Visit only.
- g. To be eligible to continue in the study, a negative serum pregnancy test must be documented at the Screening Visit. A negative urine pregnancy test must be documented at the Randomization Visit (prior to dosing), and a negative serum pregnancy test must be documented at the Week 12/End-of-Treatment Period (EOT) Visit.
- h. Study coordinator will instruct patients about the use of laxatives, suppositories, and enemas (refer to [Appendix II](#)).
- i. All AEs occurring after the patient signs the ICF will be captured. Appropriate site personnel will complete a follow-up phone call to patients within 48 hours following initial study drug administration to assess for developing AEs. The Sponsor will perform a blinded review of the safety information obtained from the first 40 follow-up phone calls, and determine whether follow-up phone calls to patients should continue or be discontinued. (See [Follow-up Phone Call Section](#))
- j. At the Pretreatment Visit and all subsequent visits, the study coordinator will register the patient visit to the clinic in the patient's eDiary. At the Pretreatment Visit, the study coordinator will instruct the patients about the use of the eDiary. Refer to the eDiary User Manual.
- k. An eDiary will be used for recording Daily BM-related Symptom Severity Assessments, Daily abdominal Symptom-severity Assessments, Weekly Assessments, EQ-5D, Treatment Satisfaction, Assessment, SF-MPQ-2, SF-12-v2, IBS-SSS, and any use of rescue medicine. Patients will enter BMs and rescue medicine in the eDiary on an event-driven basis, and will complete an evening entry each day to record daily assessments.
- l. At the Randomization Visit and all subsequent visits, the study coordinator will review the eDiary entry information to verify patient compliance with the daily eDiary completion requirement. After determining the patient's compliance, the study coordinator will remind patients to complete the eDiary daily (except at the EOT visit). (eDiary questions may be found in the eDiary User Manual.)
- m. Rescue Medicine (oral bisacodyl or bisacodyl suppositories) will be supplied to patients at the Pretreatment Visit and, if needed, at subsequent study drug dispensing visits.
- n. Study drug will be administered in the clinic at the Randomization Visit (study drug does not need to be taken in the morning before breakfast). Patients are instructed to fast for 2 hours before this clinic visit. On all other days, study drug will be taken once daily in the morning at least 30 minutes before breakfast.
- o. Patients who are randomized but do not complete the Treatment Period (withdraw consent or are discontinued before they have completed 12 weeks of treatment), will be considered Treatment Period withdrawals and should complete the procedures required at the EOT Visit (even if out of window).

### ***Screening Visit (Visit 1)***

At the Screening Visit, a review of Inclusion and Exclusion Criteria will be conducted to determine the patient's eligibility for progression to the Pretreatment Period. Overall eligibility should be determined by the investigator or an appropriately trained health professional listed on Form FDA 1572. Study procedures will be reviewed with the patient, the caregiver, and the patient's legally authorized representative (LAR: if different from the caregiver); and documentation of informed consent will be obtained. After the patient signs the ICF, the study coordinator will access IWRS to register the patient's Screening Visit, and the patient will then be assigned a unique PID number in sequential order. The following procedures will be performed thereafter:

- Medical history
- Physical examination
  - A physical examination should include all assessments (general appearance, HEENT [head, ears, eyes, nose and throat], neck, cardiovascular, thorax/lungs, breasts, abdomen, rectal, genitourinary, musculoskeletal, lymph nodes, skin, neurologic and mental status).
  - A rectal examination should be performed during the Screening Period in all patients who do not require a colonoscopy (refer to [Appendix III](#)). After the Screening Period, the rectal examination is optional and may be performed at the discretion of the investigator.
  - The breast and genitourinary examinations are optional at the discretion of the investigator.
- Body weight and height
- Seated vital signs
- Documentation of prior and concomitant medicines, including investigational products and past use of tegaserod (Zelnorm®), prucalopride, plecanatide, linaclotide (Linzess®), and lubiprostone (Amitiza®)
- Collection of blood and urine samples for clinical laboratory determinations
  - Clinical chemistry
  - Complete blood count (CBC)
  - Urine drug screen
- Serum pregnancy test (result must be confirmed as negative in order to qualify for study participation)

- Instructions given for patients to discontinue the use of all laxatives, suppositories and/or enemas at least one calendar day before the first day of the Pretreatment Period, and all other prohibited medicines (as defined in [Appendix II](#)) at least 14 calendar days before the first day of the Pretreatment Period.
- Patient reminder (schedule patient's next visit and remind the patient to refrain from using prohibited medicines as described in [Appendix II](#))

### ***Pretreatment Visit (Visit 2)***

The Pretreatment Period will occur between 14 and 21 days immediately before the Randomization Visit. The purposes of this period are to collect Pretreatment Period data to determine whether the patient is eligible to continue into the Treatment Period of the study, to provide the patient with experience using the data collection methods employed during the study (i.e., eDiary), and for comparison with data collected during the Treatment Period.

The study coordinator will access IWRS to register the patient's Pretreatment Visit. At the Pretreatment Visit, which will occur between Day -21 and Day -14 (inclusive), the Inclusion and Exclusion Criteria will again be reviewed, study procedures will be explained to the patient, and the following will be performed:

- Verification that Inclusion and Exclusion Criteria continue to be met
- Body weight
- Seated vital signs
- Documentation of concomitant medicines
- Review of AEs, from the signing of the ICF to Visit 2
- Register visit in eDiary
- eDiary training (patients will be instructed on the use of eDiary) and the assessments that will be collected as listed below:
  - Daily BM-related Symptom-severity Assessments on an event-driven basis (frequency, consistency, straining and completeness)
  - Daily Abdominal Symptom-severity Assessments in a daily evening report (abdominal bloating, abdominal discomfort, and abdominal pain)

- Use of Per-protocol Rescue Medicine or any other Laxatives, Suppositories, and Enemas on an event-driven basis
- Weekly Patient Assessment of Constipation Severity
- Weekly Patient Assessment of IBS Symptom Severity
- Weekly Patient Assessment of Adequate Relief
- Dispensing of Rescue Medicine; review with patient how Rescue Medicine should be used
- Patient reminder (schedule patient's next visit and remind the patient to refrain from using prohibited medicines and to refrain from using Rescue Medicine the calendar day before and day of the Randomization Visit)

### ***Randomization Visit (Visit 3)***

At the Randomization Visit, the Inclusion and Exclusion Criteria will again be reviewed to confirm the patient's eligibility. At this visit, the study coordinator will register the Randomization Visit on the patient's eDiary, and the patient will respond to the required assessments on the eDiary in the clinic. After the patient completes the eDiary entry, the study coordinator will access the eDiary website to confirm the patient's eligibility. If the patient's eligibility is confirmed in the eDiary website and all Inclusion and Exclusion criteria are met (reference below bulleted procedures to be completed prior to randomization), the study coordinator will confirm on the eDiary that the patient is randomized. The study coordinator will then register the Randomization Visit in IWRS, and the IWRS will assign a randomization number. Once the necessary procedures are completed (reference below bulleted procedures to be completed after randomization but prior to first dose), each eligible patient will be administered study drug (initial doses) in the clinic. The patient will be dispensed two bottles containing double-blind study drug (one bottle containing tablets and one bottle containing capsules) for the first four weeks of the Treatment Period. The study coordinator will perform the appropriate procedures after study drug administration, including review of the study procedures with the patient and instruct the patient to continue to complete the eDiary daily.

The following procedures will be performed before randomization and administration of the first dose of study drug at the study center:

- Verification that Inclusion and Exclusion Criteria continue to be met

- Body weight
- Seated vital signs
- Documentation of concomitant medicines
- Collection of blood for clinical laboratory determinations
  - Clinical chemistry
  - CBC
- Urine pregnancy test (result must be confirmed as negative before randomization and the administration of the first dose of study drug)
- Review of AEs
- eDiary compliance verification (study coordinator will verify the patient's compliance with the daily entry requirement) and eDiary entry in the clinic, including the following assessments:
  - Daily BM-related Symptom-severity Assessments on an event-driven basis
  - Daily Abdominal Symptom-severity Assessments in a daily evening report
  - Use of Per-protocol Rescue Medicine or any other Laxatives, Suppositories, and Enemas on an event-driven basis
  - Weekly Patient Assessment of Constipation Severity
  - Weekly Patient Assessment of IBS Symptom Severity
  - Weekly Patient Assessment of Adequate Relief

In addition, the study coordinator will verify the patient's compliance with the eDiary entry requirement during the Pretreatment Period and remind the patient to complete his or her eDiary entry each day.

The following procedures will be performed after randomization (prior to first dose):

- SF-12v2 (Short Form-12 Health Survey version 2 [self-administered by the patient; [Appendix VII](#)])
- EQ-5D (EuroQoL-5 Dimension [self-administered by the patient; [Appendix VIII](#)])
- SF-MPQ-2 (Short-Form McGill Pain Questionnaire-2 [self-administered by the patient; [Appendix IX](#)])
- IBS-SSS (Irritable Bowel Syndrome-Symptom Severity Scale [self-administered by the patient; [Appendix X](#)])

- Study drug (initial doses) administered in the clinic

The following procedures will be performed after study drug administration:

- Dispensing of study drug - one bottle containing 34 tablets (one bottle = 35 tablets less the initial dose) and one bottle containing 34 capsules (one bottle = 35 capsules less the initial dose)
- eDiary entry reminder (patients will be instructed to complete eDiary throughout the day of the Randomization Visit and reminded to complete eDiary entry each day thereafter)
- Dispensing of Rescue Medicine, as needed; review with patient how Rescue Medicine should be used
- Patient reminders (schedule patient's next visit and remind the patient to refrain from using prohibited medicines and to refrain from using Rescue Medicine for the remainder of the day of randomization and for the calendar day after randomization)

### ***Follow-up Phone Call (Day 3)***

Appropriate site personnel will complete a follow-up phone call to patients within 48 hours following initial study drug administration to assess for developing AEs. In doing this, patients will be asked the same nonleading question that is asked at the study visits. (See Section 5.5.3.2.1) Any AE reported during the phone call will be captured on the eCRF. Patients who report AEs during the follow-up phone call will be provided with instructions on the appropriate follow-up care. The Sponsor will perform a blinded review of the safety information obtained from the first 40 follow-up phone calls. If the safety information from the phone calls is consistent with the known safety profile of the IR formulation of linaclotide (LINZESS® 290 µg in IBS-C), then no further follow-up phone calls will be made to patients. The Sponsor will communicate accordingly to the clinical sites to indicate whether follow-up phone calls to patients should continue or be discontinued.

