Linaclotide was well-tolerated in these trials.  There were no deaths. One patient died during the Screening Period but never received either linaclotide or placebo. There were a total of 15 SAEs in the two trials. There were 9 (1.1%) SAEs in placebo-treated patients and 6 (0.7%) SAEs in linaclotide-treated patients. Overall, there was no obvious pattern in the types of SAEs experienced in either the placebo or linaclotide group. There were no SAEs of diarrhea. Treatment-emergent AEs (TEAEs) occurred in 54.9% of placebo-treated and 60.8% of linaclotide-treated patients. Diarrhea was the most frequent TEAE and was reported in 3.0% of patients treated with placebo and 19.8% of patients treated with linaclotide. Diarrhea was generally mild to moderate in severity. Diarrhea resulted in the discontinuation of 0.4% of patients treated with placebo and 5.3% treated with linaclotide. Human studies have not been conducted with the DR formulations of linaclotide. As the IR and DR formulations have the

same active ingredient, similar gastrointestinal side effects (diarrhea, abdominal pain, abdominal distension, and flatulence) may be expected. However, the frequency and severity of these effects remain to be determined.

Refer to the Investigator's Brochure for a more detailed description of the chemistry, pharmacology, efficacy, and safety of linaclotide, based on studies conducted in animals, healthy volunteers, and in patients with IBS-C and CIC and its relevance to the delayed release formulations.

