#### **5.4.3 Method of Assigning Patients to Treatment Groups**

The patient identification (PID) number will consist of seven digits; the first three digits represent the study center number, followed by a one-digit study indicator ('4') and a three-digit patient number assigned in an ascending sequential order, beginning with 001, 002, etc. The patient will retain the same PID number (which is also the Screening Number) throughout the Treatment Period.

Patients who meet all of the inclusion criteria and none of the exclusion criteria will be randomized into the study at the Randomization Visit on Day 1. Approximately 520 patients will be randomized in equal proportions to one of eight treatments (as described in Section [5.4.1](#)). Randomization numbers will be assigned by interactive web response system (IWRS).

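### Is a blinded review of 40 calls, about five per arm, too weak a basis for ending the Day 3 safety calls?

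*Protocol*

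**What the plan says.** Under Follow-up Phone Call (Day 3) in Protocol section 5.5.1, site staff are to "complete a follow-up phone call to patients within 48 hours following initial study drug administration" and ask the same open question about adverse events that is used at visits. The sponsor then looks at the early calls: "The Sponsor will perform a blinded review of the safety information obtained from the first 40 follow-up phone calls". The condition is "If the safety information from the phone calls is consistent with the known safety profile of the IR formulation of linaclotide" at 290 µg in IBS-C; where it is met, "then no further follow-up phone calls will be made to patients". The sponsor tells sites whether to continue or stop.

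Protocol section 5.5.3.2.1 repeats the rule. The Synopsis, footnote i of the Schedule of Evaluations and footnote i of SAP Table 2 mention the review. None of these places gives a count, a rate, a severity criterion or a 48-hour reference figure.

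Two pieces of background matter. Protocol section 5.4.3 states: "Approximately 520 patients will be randomized in equal proportions to one of eight treatments". The Introduction says of the new formulations: "Human studies have not been conducted with the DR formulations of linaclotide". On the IR registration trials it says: "Diarrhea was the most frequent TEAE and was reported in 3.0% of patients treated with placebo and 19.8% of patients treated with linaclotide".

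**The concern.** The call is the only scheduled contact between Day 1 and the Week 4 visit in the first clinical study of two new formulations. No interim comparison of arms is planned (Protocol 5.7.10, SAP 6.4).

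The review that can end the calls covers about five patients per arm, and about ten of the 40 are on placebo or the approved product. It is blinded, so arms are seen together. Its benchmark is a profile whose only quoted frequencies come from trials of 12 and 26 weeks, while the calls cover 48 hours.

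A high rate of early diarrhea in one DR arm could be diluted by the other seven, set against a figure accumulated over months, and judged consistent. The calls would then stop on a reassurance that the data cannot give about any single DR regimen.

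**Working it through.** The plan attaches no threshold or error rate to this review, so there is no figure of its own to reproduce. What follows measures the review's sensitivity under stated assumptions.

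**Inputs.** 40 calls, blinded (Protocol 5.5.1); 8 equal arms and about 520 patients (5.4.3); diarrhea 3.0% on placebo and 19.8% on IR (Introduction); about 80 sites (section 2).

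**Step 1: numbers per arm.** 40/8 = 5 expected per arm: 5 placebo, 5 IR, 30 over the six DR arms. Patients not called if the calls stop: 520 − 40 = 480.

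**Step 2: pooled diarrhea rate.** For the moment, treat 3.0% and 19.8% as if they applied to the call window.
- All seven active arms at the IR rate: (5 × 0.03 + 35 × 0.198)/40 = 7.08/40 = 17.7%.
- One DR arm at rate p, other active arms at the IR rate: (5 × 0.03 + 30 × 0.198 + 5p)/40 = (6.09 + 5p)/40.
- One DR arm at 100% and no diarrhea in the other 35 patients: 5/40 = 12.5%. This is the only one of these cases in which a 100% arm stays below 19.8%, and it requires no diarrhea even among the IR patients.

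**Step 3: chance of a flag.** Assume a one-sided 5% rule. It flags at 12 or more of 40 if the reference is the expected mix of arms (actual size 3.8%), and at 13 or more if the reference is 19.8% in all 40 (4.0%). Exact binomial sums, five per arm, other DR arms at the IR rate:

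| Rate in one DR arm | Expected count | Pooled rate | Flagged (13+ to 12+) |
|---|---|---|---|
| 40% | 8.09 | 20.2% | 4-9% |
| 60% | 9.09 | 22.7% | 9-16% |
| 80% | 10.09 | 25.2% | 16-27% |
| 100% | 11.09 | 27.7% | 25-41% |

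So an arm at 60% passes 84-91% of the time, and an arm at 100% passes 59-75%. If the other five DR arms sit at the placebo rate, a 100% arm gives 0.15 + 0.99 + 0.75 + 5 = 6.89 of 40 (17.2%) and is flagged about 0.2% of the time or less.

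**Step 4: a matching time window.** The documents give no 48-hour rate. Suppose a fraction f of the IR and placebo diarrhea starts within 48 hours, and the reviewer allows for that. The same 5% rule then gives:

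| Assumed f | Flag at | DR arm at 60% within 48 h | DR arm at 100% within 48 h |
|---|---|---|---|
| 0.10 | 3 or more | 80% | 100% |
| 0.25 | 5 or more | 49% | 100% |
| 0.50 | 8 or more | 22% | 60% |

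If the 48-hour counts were instead held against 19.8%, these arms would be flagged 1% of the time or less. The answer depends mainly on the reference the reviewer uses.

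**Step 5: events outside the IR profile.** Here one case is enough, and blinding does not hide it. The Introduction reports no serious diarrhea events with IR, so a single one would be off-profile. The chance of at least one case among five patients is 1 − (1 − p)^5: 23% at p = 5%, 41% at 10%, 67% at 20%, 83% at 30%. It passes one half at p = 1 − 0.5^(1/5) = 13%. For an event occurring at 10% in all six DR arms, 1 − 0.9^30 = 96%.

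**Step 6: what depends on the calls.** Adverse events are still asked about at Weeks 4, 8 and 12 and recorded from any other communication; serious events go to the sponsor within 24 hours (Protocol 5.5.3.2.1). Intolerable events have an interruption and Medical Monitor route (5.3.3). Stool form and abdominal symptoms are entered in the eDiary throughout. The final safety tables are by treatment group, including time to first diarrhea (SAP 7.11.1). Which patients are called depends on order of entry, not on arm, so ending the calls does not favor one arm in those comparisons.

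**The case for a change.** The strongest case for a change is that the review asks the wrong question. Whether 40 pooled patients resemble IR says little about whether one DR dose does. Five per arm is itself only an expectation, because no block size is given; under simple randomization, some arm would have two or fewer of the first 40 calls about 66% of the time. No cases in five patients leaves a one-sided 95% upper limit of 45%. Spontaneous reports and 24-hour serious event reporting do not replace a direct question, and the eDiary serves efficacy. Keeping the calls would cost about 480 short contacts, 480/80 = 6 per site.

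Much of this stands. The review is insensitive to an excess of an expected event in one arm, and neither the criterion for consistency nor the 48-hour reference is written down.

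What does not stand is the step to a fault in the plan. The protocol contains no 19.8% cut-off; the sponsor's reviewers also have the severity, causality and seriousness assessment recorded for each event. It is not credible that five cases of severe diarrhea in 40 would be waved through because 12.5% is below 19.8%. Nor do the alternatives clearly improve matters. Calling everyone is a choice about monitoring intensity. Tabulating by arm would bring an unblinded look and an unblinded reviewer into a trial that plans neither, still with no decision rule. Waiting for 20 patients per arm lowers the chance of seeing no case of a 10% event from 0.9^5 = 59% to 0.9^20 = 12%, but one case of an expected event such as diarrhea is not a signal.

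**Conclusion.** No change to the plan follows. The arithmetic supports a limited statement: under an assumed one-sided 5% flag and the protocol's 3.0% and 19.8% rates, one DR arm at 60% diarrhea passes 84-91% of the time when the other DR arms match IR. With an assumed matching 48-hour reference (f from 0.10 to 0.50), an arm at 60% within 48 hours is flagged 22-80% of the time, and one at 100% is flagged 60-100%. Off-profile events can be recognized from a single case. It is therefore not shown that a serious problem in one arm would pass, or that the calls would end whatever a DR arm did.

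The decision at stake is only whether an extra telephone contact continues. No efficacy or safety conclusion of the trial depends on it, and the other routes for reporting adverse events stay open. The unwritten criterion and 48-hour reference are details that the sponsor's medical reviewers can be expected to supply when they make the judgement. A passed review should be read as what it is, a reason to stop calling, and not as evidence on the safety of any individual DR regimen.
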